16.3 Study risk management

The following mitigations have been implemented to minimise and manage the risks arising from the deployment of the Salutare One Referral software:

- Collaborative Creation and Beta Testing of MDT Referral Form: The MDT referral form will be created in collaboration with MDT panel members and comprehensively beta tested prior to live use. This ensures that the form meets the specific needs and expectations of the panel, and any issues can be identified and resolved early.
- User-Friendly Design: The One Referral software deploys an intuitive, user-friendly design that allows users to complete referrals with minimal training. This reduces the likelihood of errors and enhances the overall user experience.

Title: Salutare Dialogue for MDTs					
Authors	[name], [name], [name]	Ver.2		Date Authorised	22/01/2025

- Instructional Video for Trial Participants: MDT panel members participating in the trial will be required to watch an instructional video. This video will explain how to complete and send a referral form, request input from others within and outside the MDT, report software issues, and what to do in the event of system unavailability. This ensures that all users are well-informed and prepared to use the software effectively.
- Back-Up System for Offline Operation: A back-up system will be implemented to create an offline copy of a list of patients who need to be discussed at an upcoming MDT. This allows the MDT to proceed even if the system is down due to a disruption in network or cloud services, ensuring continuity of operations.
- Comprehensive Application Support: Application support will be provided to address any difficulties via email and an email chat feature during working hours from 8 am to 7 pm, with responses within the same working day. If issues cannot be resolved through the video and email support, a call will be scheduled to address the problem. This ensures that users have access to timely assistance and can quickly resolve any issues they encounter.
- Regular Software Updates and Maintenance: Regular software updates and maintenance will be scheduled to ensure the system remains secure, up-to-date, and functional. These updates will address any identified vulnerabilities, improve performance, and introduce new features or improvements based on user feedback.

16.4 Adverse Event monitoring

Serious adverse events are any unfavourable and unintended signs, symptoms or a disease associated with clinical study intervention. Adverse events in IMP clinical trials are typically categorised as follows:

- Adverse Event: (AE) Any untoward medical occurrence in a patient or clinical trial subject administered a medicinal product and which does not necessarily have a causal relationship with this treatment.
- Adverse Reaction (AR) Any untoward and unintended response to an investigational medicinal product related to any dose administered.
- Serious Adverse Event (SAE) or Serious Adverse Reaction (SAR): Any adverse event or adverse reaction that: 1. Results in death 2. Is life –threatening 3. Requires inpatient hospitalisation or prolongation of existing hospitalisation 4. Results in persistent or significant disability/incapacity 5. Is a congenital anomaly/birth defect.
- Suspected Unexpected Serious Adverse Reaction (SUSAR): An adverse reaction that is both unexpected (not consistent with the applicable product information) and meets the definition of a Serious Adverse Event/Reaction.

There is limited literature and regulatory consensus on adapting the above adverse event monitoring framework for the purpose of digital intervention studies. Bradstreet (2019) reviewed adverse event monitoring in mHealth studies for psychosis interventions, concluding that monitoring and reporting of adverse events or effects is largely neglected in these studies, with majority of reviewed studies only reporting levels of acceptability, usability and/or engagement that are poor surrogates for the direct and contemporaneous assessment of adverse or unwanted experiences.

Bradstreet reports standards and outputs of the adverse event procedure used in the EMPOWER (Early signs Monitoring to Prevent relapse in psychosis and promote Wellbeing, Engagement and Recovery, ISRCTN: 99559262) feasibility study of the EMPOWER App, an mHealth intervention to enhance detection of Early Warning Signs of

Title: Salutare Dialogue for MDTs					
Authors	[name], [name], [name]	Ver.2		Date Authorised	22/01/2025

psychosis and prevent relapse. He recommends that future mHealth studies adopt a pro-active within-study process for the reporting and assessment of adverse events to improve the researcher ability to modify interventions as required and to respond adequately to safety issues as and when they arise.

Unlike the EMPOWER App, One Referral is not classed as MHRA regulated medical device. It is an information management and administration system. Nevertheless we have carried out a full risk and hazard assessment that is included withing our DCB0129/DPIA which are affixed to this submission and include full details of our risks and mitigations.

Any incidents or events related to the operations of the One Referral software, which result have resulted or could have resulted (near miss) in patient care errors, omissions or a delay in patient care provision, will be classed as SAEs and Datix reportable incidents.

In line with the standards proposed by Bradstreet (2019) as implemented in the EMPOWER trial, we will encourage participants to report all negative experiences, in particular examples or types of incidents that may occur arising or potentially arising from the One Referral software, their seriousness and intensity. All reported adverse events will be reviewed by the Chief Investigator, Principal Investigator, Clinical Safety Officer, and other delegated research team members for relatedness and severity. Each incident investigation will be accompanied by Corrective and Preventive Actions (CAPA). Unresolved critical incidents might lead to early study discontinuation.

Detailed Trial Operating Procedures (TOPs) for adverse event reporting will be adopted, detailing the study procedures to encourage study participants to report SAEs.

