16	Legal and Regulatory Requirements	24
16.1	NICE and DH requirements for Digital Health Technologies	24
16.2	Clinical safety	25
16.3	Study risk management	25
16.4	Adverse Event monitoring	26
16.5	Incident reporting	27
16.6	Confidentiality	27
16.7	Cybersecurity	28
16.8	Medical Device Regulations	28
16.9	Ethical compliance	28
17.	Quality Assurance Procedures	29
17.1	Study Monitoring	29
17.2	Protocol Deviations	29
18.	Payments and incentives	29
19.	Funding	29
20.	Indemnity	29
21.	Intellectual Property	29
22.	Presentation and publication plans	30
23.	End of Study	30
	References	31

1. Summary of Study Design

Title	Single cohort before and after mixed-methods prospective study to investigate the impact of the Salutare One Referral software on patient outcomes, safety and effectiveness of Multi-Disciplinary Team (MDT) meetings
Short Title/acronym	Salutare One Referral for MDTs
IRAS number	347710
Sponsor	Salutare Group Ltd.
Funder name & reference	Salutare Group Ltd.
Clinicaltrials.gov no	TBC
Design	A mixed-methods prospective Before and After Study
Primary objective	The primary objective is to evaluate safety, acceptability and implementation feasibility of the Salutare One Referral Software
Secondary objectives	
Determination of the following metrics with and without the use of the Salutare One Referral software:
 
 (1) MDT administration time (2) Completeness of pre-assessment information (3) Clinical engagement (4) Time spent by MDT panel members attending meetings (5) MDT performance rating (6) Duration of MDT per-patient discussion time (7) Overall time for MDT meetings (8) Time from referral submission to the generation of MDT definitive decisions. (9) Time from referral submission to the implementation of MDT recommendations (OPTIONAL) (10) Number and rate of cases re-presented for MDT review – breast cancer only (11) Drug changes to accommodate surgery or any disease optimisation advice (12) Presence or absence of peri-operative and post-operative complications (OPTIONAL)
Primary endpoint	The study aims to assess the Salutare One Referral Software's safety, implementation feasibility and users acceptability in facilitating effective MDT meetings. System Usability Score (SUS) and user questionnaires will be administered to MDT panel members, with modifications to the SUS as necessary. The primary and secondary endpoints of the study will inform future

Title: Salutare Dialogue for MDTs					

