7.2 Primary objective

The primary objective is to evaluate safety, acceptability and implementation feasibility of the Salutare One Referral Software.

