8.1 Primary Endpoint

The determination of the Salutare One Referral Software safety, implementation feasibility and user acceptability in facilitating effective MDT meetings. One Referral software System Usability Score (SUS) and user questionnaires will be administered to MDT panel members. The intent is to utilise the current study's primary endpoint to inform a future protocol amendment and study expansion to further sites to test for clinically relevant and patient relevant outcomes.

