8.3 The Study Evaluation Model

A Logic Model is used as a theory-based approach to explicitly articulate the underlying theory of change which shapes the desired outcomes and impacts achieved by the Salutare One Referral software as per the study hypothesis (Kaplan and Garrett, 2005; Hayes et al., 2011; Helitzer et al., 2010; Friedman & Wyatt 2006).

Title: Salutare Dialogue for MDTs					
Authors	[name], [name], [name]	Ver.2		Date Authorised	22/01/2025

How Salutare Dialogue can lead to better patient outcomes & NHS resource use

Key: Sources are in bold italic, eg *"Raine 2014"*

[figure not shown]

Figure 1: One Referral Logic Model

The chosen secondary endpoints are the observed clinical outputs. The study is a pilot project and therefore not powered to collect data on health outcomes mediated by the clinical outputs. Note: The patient communication module is currently not yet available and therefore will not be assessed in the present study. Observing the duration of MDT per-patient discussion time with and without One Referral contributes to understanding the software's influence on MDT efficiency. This endpoint sheds light on whether One Referral facilitates more concise and productive discussions among team members.

User questionnaires assessing MDT discussions' effectiveness and referral information completeness with and without One Referral provide further qualitative data on the software's impact. Lastly, evaluating MDT preparation time through user questionnaires offers insights into the software's efficiency in streamlining preparatory tasks.

The System Usability Score (SUS) (Brooke, 1996), the only validated tool used in this study, offers valuable insights into the acceptability of the One Referral software. SUS is a simple, widely used 10-statement survey that asks users to rate their level of agreement or disagreement to the 10 statements (half worded positively, half worded negatively) about the software under review.

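### Safety is part of the primary endpoint, but the only measures named for it are SUS and opinion questionnaires; the software incidents the protocol collects belong to no endpoint or analysis

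*Protocol*

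**What the plan says.** Protocol 7.2: "The primary objective is to evaluate safety, acceptability and implementation feasibility of the Salutare One Referral Software". Section 8.1 carries the same three components into the endpoint: "The determination of the Salutare One Referral Software safety, implementation feasibility and user acceptability in facilitating effective MDT meetings". The next sentence of 8.1 names the measures: "One Referral software System Usability Score (SUS) and user questionnaires will be administered to MDT panel members". The summary table in section 1 names the same two: "System Usability Score (SUS) and user questionnaires will be administered to MDT panel members, with modifications to the SUS as necessary".

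Section 8.3 says that SUS "offers valuable insights into the acceptability of the One Referral software" and describes it as "the only validated tool used in this study". The surveys in 11.1 and 11.3 ask for participants' views on the safety of the MDT, and the survey in 11.4 asks about gains or losses in safety once the software is withdrawn.

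Section 16.4 reports a review of mobile-health studies in psychosis. It found that most studies reported only acceptability, usability or engagement, which are "poor surrogates for the direct and contemporaneous assessment of adverse or unwanted experiences". The protocol says it will work in line with that review's standards. "Any incidents or events related to the operations of the One Referral software" that caused, or nearly caused, errors, omissions or delays in care are to be classed as SAEs and entered in Datix. They are then reviewed for relatedness and severity and followed by corrective and preventive action (CAPA). Section 16.5 asks every participant to report issues, and section 15 lists patient safety issues and near misses among the grounds for discussing early termination.

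**The concern.** A primary endpoint that includes safety needs a measure of safety. The two measures named beside it are a usability scale and questionnaires. The data that bear directly on whether the software caused harm or nearly did so are collected under a separate heading and are not connected to the endpoint.

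This matters because 8.1 uses the primary endpoint to inform a protocol amendment and expansion to further sites, 16.1 says the pilot is meant to generate evidence of safety, and section 22 foresees publication and discussions with NHS executive bodies. Followed as written, the safety part of the primary answer would consist of usability and opinion data. The incident reports would be handled operationally, with no commitment in the endpoint or analysis sections to count them against the number of cases exposed.

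**Working it through.** The plan states no figure on this point, so the main check is to set the sections side by side.

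| Place in protocol | What it offers on safety |
|---|---|
| 7.2, 8.1, section 1 summary | Safety named as a primary component; measures named are SUS and user questionnaires |
| 8.2 (12 secondary endpoints) | No software incidents. The nearest item is endpoint 12, surgical complications from medical records (optional in the section 1 summary), which is a patient outcome |
| 8.3 | SUS linked to acceptability; the only validated tool |
| 8.5 | No mention of incidents or near misses |
| 8.6 | Primary outcomes worded as members' confidence and satisfaction; safety absent |
| 11.1, 11.3, 11.4 | Opinion on MDT safety at set survey days (Days 0, 98 and 126 for the complex-case MDTs, section 13) |
| 12 | KPIs: users set up, comments, referrals processed; no incidents |
| 15, 16.4, 16.5 | Direct incident and near-miss reporting, used for investigation, CAPA and possible early termination |

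Three steps follow.

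1. On the protocol's own account SUS informs acceptability, so it does not supply the safety component.
2. The questionnaires do ask about safety. But if SUS is the only validated tool, their safety items are not validated, and they record views on set days rather than events as they occur.
3. The direct data appear only in sections 15, 16.4 and 16.5. No endpoint, KPI or analysis section takes them up.

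**Illustration of what the incident data could show.** Inputs are the target numbers of cases discussed with the software in section 1: about 40 (RNOH) and about 120 (Royal Free colorectal), together 40 + 120 = 160. The breast MDT is on hold and is left out. Assumptions: the case is the unit, cases are independent, and every incident is reported.

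With zero incidents in n cases the exact one-sided 95% upper bound is 1 − 0.05^(1/n), and the upper limit of the exact two-sided 95% interval is 1 − 0.025^(1/n).

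| n | One-sided 95% bound | Two-sided 95% upper limit |
|---|---|---|
| 40 | 1 − 0.05^(1/40) = 7.2% | 1 − 0.025^(1/40) = 8.8% |
| 160 | 1 − 0.05^(1/160) = 1.9% | 1 − 0.025^(1/160) = 2.3% |

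At RNOH alone, no incidents would still be compatible with about 1 affected case in 14 (1/0.072 ≈ 14). These bounds do not measure the defect, since they are the same whether or not 8.1 names the incidents. They show only why a bare report of no incidents needs its denominator and interval.

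**The case against.** The strongest reply is that the protocol does monitor safety directly. The criticism reported in 16.4 is aimed at studies that report nothing except acceptability, usability or engagement, and 16.4 answers it by adding incident and near-miss reporting with review and CAPA. Section 15 gives those reports real weight. All of this stands: a reader might infer that safety monitoring is missing, and the documents do not support that.

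Two other strong readings also fail. A reader might infer that the protocol rejects its own instruments. It does not: the poor-surrogate remark is a cited review's conclusion about mobile-health studies in psychosis, which the protocol reports and follows. It bears directly on SUS and less directly on questionnaires that ask about safety. A reader might also infer that safety will be judged by SUS alone. Section 8.1 does not say so; it lists three components, then two instruments, without matching them or calling the list complete.

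It can also be said that denominators, intervals and tables by MDT may sit in an SAP that is not shown. That is fair for those details. It does not cover the choice of measure: the protocol itself fixes the primary endpoint and names its instruments, and an SAP should not have to supply the measure for one of its components.

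Lastly, the zero-event bounds reflect the size of a descriptive pilot, and independence is doubtful because one outage could affect a whole meeting list. Both points are accepted, which is why the figures serve only as illustration.

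**Conclusion.** The point holds as a gap in the endpoint definition. Safety is a primary component, but the measures named with it are a usability scale that 8.3 assigns to acceptability and questionnaires that gather periodic, unvalidated opinion. The direct evidence the protocol already collects is not linked to the primary endpoint, the secondary endpoints, the KPIs or the analysis, and 8.6 describes the primary outcomes without safety at all.

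The conclusion rests on the text of 7.2, 8.1 to 8.3, 8.5, 8.6, 12, 16.4 and 16.5, and on no numerical assumption. It should be corrected, but it is a matter of linking existing data to the endpoint, not a failure to monitor safety.

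**What to change.** In 8.1 and 8.5, name the safety component of the primary endpoint: the number of software-related incidents and near misses, as defined in 16.4, in the intervention phase, per case handled with the software. Report it by MDT and pooled, with an exact 95% CI and a short description of each event. The denominator should be cases actually handled with the software, because section 15 allows members to fall back on the existing referral route.

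Keep SUS as the measure of acceptability and treat the questionnaire views on safety as supportive. Reword the primary outcomes in 8.6 to agree with 8.1.

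The cost is wording plus a small table, since incident reports (16.4, 16.5) and counts of referrals processed (section 12) are already collected. A comparison of incidents of any cause across all phases is not proposed: 16.4 covers only software-related events, so it would require a new data extraction.

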16.5 Incident reporting

An incident reporting process has been implemented. All study participants will be asked to report any suspected or actual issues to the research team for investigation and resolution. The Salutare research team operates an incident reporting system and provides support within working hours, between 9:00 and 17:00 Hrs. An Out-of-hours IT support is provided by the participating NHS Trust IT service desk, as per standard arrangements.

16.6 Confidentiality

All information collected about study participants in relation to this study will be kept strictly confidential. All participants will be assigned a non-identifiable study number and the data collected in the study will be linked to this number. The study participation itself cannot be kept confidential as the study participants might need to engage with the Salutare study research team. Their participation will also be known to other study participants as they will interact daily as part of the MDT panels.

MDT meetings will be observed (either directly or via reviewing MDT meeting transcripts) by NHS researchers to collect data on the MDT review duration, quality and outcomes. This data will be pseudonymized by NHS researchers.

The patient information processed by the One Referral system includes information required to complete an MDT referral. This includes five key sections for each referral, plus any additional information the referrer wishes to provide. It should be noted that images and histology are not accessed through the platform, but the system is a means to allow transfer requests.

Title: Salutare Dialogue for MDTs					
Authors	[name], [name], [name]	Ver.2		Date Authorised	22/01/2025

1. Brief medical history
2. Details of prior MDT discussions, treatments, or relevant history
3. The question or questions being asked to the MDT
4. Whether the patient is aware of the referral to the MDT
5. An assessment of frailty or fitness of the patient

This data will be processed for the purpose of direct care provision.

16.7 Cybersecurity

The One Referral software is fully compliant with the Data Security and Protection Toolkit (DSPT) standards. We prioritise the security and privacy of our users by implementing robust cybersecurity measures, including:

- Data Encryption: All data in transit and at rest is encrypted using industry-standard protocols to ensure confidentiality.
- Access Controls: Strict access controls are in place, ensuring that only authorised personnel can access sensitive information.
- Regular Audits: We conduct regular security audits and vulnerability assessments to identify and address potential threats.
- Incident Response: A comprehensive incident response plan is established to promptly address and mitigate any security incidents.
- Compliance: Our platform adheres to all relevant regulatory requirements and best practices to ensure the highest level of data protection.

By maintaining these stringent security measures, we ensure the safety and integrity of our users' data.

16.8 Medical Device Regulations

The existing One Referral software does not fall under the definition of software that is considered to be a medical device, as defined by the Medicines and Healthcare Products Regulatory Agency (MHRA). As such, it is excluded from medical device regulations. Therefore, this research study is not considered a clinical investigation aimed to access patient data for the generation of clinical evidence for CE marking and is not required to be registered with the MHRA. Ethics approval is sought through the Health Research Authority (HRA).

16.9 Ethical compliance

The study will only commence once evidence of Health Research Authority (HRA) approval is in place. This study will adhere to the principles outlined in the NHS Research Governance Framework for Health and Social Care and the principles of good clinical practice. It will be conducted in compliance with the protocol, the Data Protection Act and other regulatory requirements as appropriate. In conducting the study, the sponsor shall comply with all laws and statutes as amended from time to time, applicable to the performance of the study.

Title: Salutare Dialogue for MDTs					
Authors	[name], [name], [name]	Ver.2		Date Authorised	22/01/2025
Page 28 of 32					

17. Quality Assurance Procedures

The Sponsor Quality Assurance Manager will provide the study monitoring plan. Access will also be granted to the authorised representatives of the inspecting regulatory bodies, the Sponsor organisations, and the funding body, to ensure the study maintains protocol and regulatory compliance and adherence to Standard operational procedures and local policies.

